4. PARTICIPANT SELECTION AND WITHDRAWAL CRITERIA

Participants will be assigned to study drug only if they meet all the inclusion criteria and none of the exclusion criteria. Central eligibility review of diagnosis will be performed as described in Section 3.1.9.

Participation in the optional PET imaging procedures will be allowed according to local country regulations.

4.1. Inclusion Criteria

Each participant must meet all of the following criteria to be enrolled in this study:

Key clinical inclusion criteria for the study:

- 1. Participant must be in the Alzheimer's continuum as defined by the 2018 NIA-AA Research Framework (Jack 2018); this requires evidence of cerebral amyloidosis (A+). This evidence requirement can be satisfied by any one of the following 3 pathways:
 - a. Historical Amyloid PET may be allowed to fulfill this criterion if it meets all of the following:
 - i. Must utilize either [18F]florbetaben, [18F]florbetapir, or [18F]flutametamol.
 - ii. Must have adequate scan parameters and image quality as determined by the central imaging reader.
 - iii. Must have the raw data available to send to the core PET laboratory.
 - iv. Must have been read as positive (elevated amyloid) by the core PET laboratory.
 - b. Historical CSF measurements may be allowed to fulfill this criterion after review by the Medical Monitor. At a minimum, documentation of historical CSF testing must contain the following details:
 - i. Identification of which laboratory did the testing.
 - ii. Identity of the type of assay used (eg, Roche Elecsys, Fujirebio Lumipulse, Athena ADMark).
 - iii. Reference ranges for the values reported.
 - c. If historical testing is not available, the participant must undergo a 2-step verification of amyloid positivity:
 - i. As an initial screen for cerebral amyloidosis, the participant must have a high or intermediate APS as measured by the PrecivityADTM Aβ blood test. Participants with a low APS are not eligible for study participation. (Note: Historical studies that do not meet the full criteria in a. or b. may still be considered sufficient, after consultation with the Medical Monitor, to allow a participant to forego PrecivityADTM screening and thus allow the participant to proceed to steps outlined in 1.c.ii amyloid confirmation.).
 - ii. Participants need confirmation of amyloid positivity with either:
 - o New positive Amyloid PET scan (see Table 2, footnote a).

AL002 Alector, Inc.

- O New positive CSF pTau/Aβ42 (see Table 2, footnote b).
- Participants who do not have confirmation of amyloid pathology based on an initial Amyloid PET scan may opt to have a second assessment with CSF. Participants who do not have confirmation of amyloid pathology on an initial CSF pTau/Aβ42 measurement may opt to have a second assessment with an Amyloid PET scan (Table 2).

Table 2: Amyloid Positivity for Study Eligibility

Initial Confirmatory Test	Second Assessment, if Initial Test is Negative	Third Assessment, if Second Assessment is Negative
Historical positive Amyloid PET ≤24 months prior to screening start	NA	NA
Historical CSF positive amyloid	NA	NA
PrecivityAD™ positive, followed by new Amyloid PET ^a	New CSF pTau/Aβ42 ^b	Not allowed; participant not eligible
PrecivityAD™ positive, followed by new CSF pTau/Aβ42°	New Amyloid PET ^a	Not allowed; participant not eligible

Aβ42=amyloid beta (1-42); CSF=cerebrospinal fluid; NA=not applicable; PET=positron emission tomography; pTau=phosphorylated Tau.

- 2. Participants must demonstrate a clinical severity consistent with Stages 2, 3, or early Stage 4 as defined in the 2018 NIA-AA Research Framework, also described as mild cognitive impairment and mild dementia in the 2018 NIA-AA Research Framework. Further, participants must meet the following inclusion criteria to define clinical severity:
 - a. Participant has mild symptomatology as defined by a screening MMSE score of ≥20 points.
 - b. Participant has a CDR-GS of 0.5 to 1.0.
 - c. Participant has evidence of episodic memory impairment as demonstrated by the RBANS-Update DMI score:
 - i. If the DMI score is ≤85, the participant meets this requirement without additional evidence needed.
 - ii. If the DMI >85 and ≤95, the participant may still be considered for participation if they have a history of cognitive and functional decline consistent with diagnosis of Early AD. Agreement between the Investigator and the Medical Monitor that the participant meets criteria for clinical severity consistent with mild cognitive impairment or mild dementia due to Early AD must be documented prior to randomization.
- 3. If the participant is receiving symptomatic AD medications (for memory and/or behavioral symptoms), the dosing regimen must have been stable for 60 days prior to screening and not expected to change during study participation.

^a Alector may decline performing a new Amyloid PET if participant has a negative historical Amyloid PET that was performed ≤12 months prior to the start of screening.

^b The CSF pTau/Aβ42 ratio will be measured by the Roche Elecsys assay and will be considered positive with a ratio of >0.024.

AL002 Alector, Inc.

General inclusion criteria for the study:

4. Participant is willing and able to give informed consent. Where not permitted by local regulations, participants deemed not able to provide informed consent by the Investigator will not be enrolled. Where local regulations permit inclusion of participants deemed not able to provide informed consent, a legally authorized representative must provide informed consent on his or her behalf, and the participant must provide assent, in accordance with the local regulations, guidelines, and institutional review board (IRB) or independent ethics committee (IEC).

- 5. Participant can be male or female, and is 50 to 85 years of age, inclusive.
- 6. Participant weighs ≤120 kg; body mass index (BMI) is between 18.5 and 34.9 inclusive.
- 7. At screening, female participants must be nonpregnant and nonlactating, and 1 of the following conditions must apply:
 - a. Participant is not a woman of childbearing potential (WOCBP) (either surgically sterilized, or physiologically incapable of becoming pregnant, or at least 1-year postmenopausal [amenorrhea duration of 12 consecutive months with no identified cause other than menopause]).
 - b. Participant is a WOCBP and agrees to use an acceptable contraceptive method from screening until 12 weeks after the last dose of study drug. Acceptable contraception is defined as using hormonal contraceptives or an intrauterine device combined with at least 1 of the following forms of contraception: a diaphragm or cervical cap, or a condom, or the sole sexual partner to a vasectomized male. Vasectomized males must have received medical assessment of surgical success. In addition, total abstinence, in accordance with the lifestyle of the participant, is acceptable.
 - c. A WOCBP must have a serum pregnancy test conducted at screening. Additional requirements for pregnancy testing during and after study intervention are described in the Schedules of Assessments (Section 14.1).
- 8. Male participants must agree to use acceptable contraception and not donate sperm from screening until 12 weeks after the last dose of study drug. Acceptable contraception for the male participant when having sexual intercourse with a WOCBP who is not currently pregnant is defined as using a condom. In addition, WOCBP partners must use hormonal contraceptives or an intrauterine device. Vasectomized male participants should have received medical assessment of surgical success.
- 9. Participant has availability of a person ("study partner") who, in the Investigator's opinion, has frequent and sufficient contact with the participant (eg, approximately 10 hours per week of in person contact), is able to provide accurate information regarding the participant's cognitive and functional abilities, agrees to provide information at clinic visits (which require partner input for scale completion), and signs the necessary consent form.
 - a. The study partner must have sufficient cognitive capacity, in the Investigator's opinion, to accurately report upon the participant's behavior, cognitive, and functional abilities. The study partner should be in sufficiently good general health, in the Investigator's opinion, to have a high likelihood of maintaining the same level of

Alector, Inc.

- interaction with the participant and participation in study procedures throughout the study duration.
- b. Every effort should be made to have the same study partner participate throughout the duration of the study.
- 10. Participant and study partner are fluent in the language of the tests used at the study site as assessed by site personnel.
- 11. Participant is willing and able to complete all aspects of the study (including MRI, LP, genotyping, and PET imaging, as applicable). The participant should be capable of completing assessments either alone or with the help of the study partner.
- 12. Participant has adequate visual and auditory acuity, in the Investigator's opinion, sufficient to perform the neuropsychological testing (corrective lenses and hearing aids are permitted).
- 13. Participant agrees not to donate blood or blood products for transfusion for the duration of the study and for 1 year after the final dose of study drug.

Inclusion criteria for participants participating in the optional Tau PET imaging assessment with [18F]MK-6240 only:

- 14. Participant has not had excessive radiation exposure prior to enrollment in the trial, as defined by local standards.
- 15. [¹⁸F]MK-6240 is available to the PET imaging center based on manufacturing distribution network and local regulations.

Inclusion criteria for participants participating in the optional longitudinal Amyloid PET imaging assessment only:

- 16. Participant has not had excessive radiation exposure prior to enrollment in the trial, as defined by local standards.
- 17. An approved amyloid radiotracer is available to the PET imaging center based on manufacturing distribution network and local regulations.

Inclusion criteria for participants participating in the optional at-home and/or in-clinic WLSA only:

- 18. For at-home participation
 - a. Participant has an available and willing study partner to administer the WLSA.
 - b. Participant has WiFi access in their residence or WiFi access in a nonpublic area where the at-home testing can take place.
 - c. Participant has access to an iPad or iPhone.
- 19. For at-home and in-clinic participation, participant is proficient in and from an English, French-, German-, or Spanish-speaking country.

AL002 Alector, Inc.

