- Participants will be randomized prior to undergoing procedures or assessments at the Predose Baseline Visit and Day 1 Visit. Participants who have provided consent to participate in the optional Tau PET imaging, optional longitudinal Amyloid PET imaging (if applicable), optional LP for CSF collection (if applicable) and/or optional WLSA will be randomized prior to the Predose Baseline Visit. Participants who will not be participating in the optional assessments will be randomized prior to the Day 1 Visit.
- ^m AEs, AESI, and SAEs will be assessed after the participant signs the informed consent until the end of study participation. Any unresolved AEs, AESI, and SAEs will be followed up through resolution or return to baseline. Additionally, SAEs considered related to study drug, [18F]MK-6240 radiotracer which occur at any time during the study will be reported until resolution, participant withdrawal of consent, loss to follow-up, or death, whichever is applicable. Definitions describing what is and is not considered an AE are provided in Section 7.1.
- ⁿ Triplicate 12-lead ECGs will be obtained approximately 1-3 minutes apart and before blood draws (predose) on appropriate days. Each ECG must be performed after the participant has been resting (supine) for at least 10 minutes.
- O A WOCBP must have a negative serum pregnancy test at screening. Additional blood or urine tests will be performed for further confirmation of nonchildbearing potential if required by local regulations, guidelines, or the institutional review board/independent ethics committee.
- ^p Urine pregnancy test (for WOCBP only) and vital signs will be performed and concomitant medications and AEs will start being collected at the Predose Baseline Visit and subsequent visits for those participants participating in a Tau PET scan.
- q Hematology includes hemoglobin, hematocrit, mean corpuscular hemoglobin, mean corpuscular volume, mean corpuscular hemoglobin concentration, white blood cells, red blood cells, platelet count, and differential count (neutrophils, lymphocytes, monocytes, basophils, eosinophils, other cells).

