Study drug administration			X		x	х	X	х	х	x	х	x	X	X	X	X	х	x	X	x	х	X	х	X	х	х			
Adverse events ^{j,q}	X	$\mathbf{x}^{\mathbf{k}}$	х	Х	х	х	xrr	х	х	Х	х	X	х	х	х	х	х	х	х	X	х	X	X	X	X	х	\mathbf{x}^{l}	х	Х
ECG (triplicate) ^{j,r,pp}	X		х		х		х			Х						х							X					х	
Pregnancy test (if applicable) ^s	X	$\mathbf{x}^{\mathbf{k}}$														$\mathbf{x}^{\mathbf{k}}$					$\mathbf{x}^{\mathbf{k}}$						x ^t	x ^t	\mathbf{x}^{t}
Thyroid function	Х																												
Folic acid and vitamin B12 levels	х																												
Hematology ^{h,u} and chemistry ^{h,v}	х		х				х				х			Х			х						х					x	x
Coagulation ^{h,w}	Х														х					x ⁿⁿ									Х
Urinalysis ^{h,x}	Х		х								х						х						х					х	X
C-SSRS ^h			Х							х						х					х		X			Х	x ^y	х	x ^y
MRI (safety, PD) ^{h,ll}	xz				х	х	х			Х						х					х					Х			
$CDR^{h,aa}$	Х									Х						х					х					Х	x ^y		x ^y
MMSE ^{h,aa}	Х									х						х					х					Х	x ^y		x ^y

AL002 Alector, Inc.

Table 9: Schedule of Assessments – Part 1 (Study Week 9 and Following) and Part 2 (All Visits) (Continued)

Study Period	Screening (Days -78 to -23) ^{ss}	Predose Baseline (Days -22 to -1)											Т	`reat	ment													1 p	
Study Week ^a			1 (D1)	3 (D15)	5 (D29)	9 (D57)	13	17	21	25	29	33	37	41	45	49	53	57	19	65 and 69	73	77	81	85	89 and 93	76	EFU/4 weeks ^{qq}	SFU/8 weeks ^d	ET
Visit Window ⁰⁰			p ⊊∓	±5d	±5d	±5d	p ⊊∓	p ⊊∓	±5d	p ⊊∓	₽ 2∓	±5d	±5d	±5d	p ⊊∓	p ⊊∓	p⊊∓	p⊊∓	p ⊊∓										
		Part	2 onl	y	•								For	parti	cipar	its ra	ndo	mize	d un	der P	arts	1 an	nd 2					•	
ADAS-Cog13 ^{h,aa}			x							х						X					х					Х	xy		x ^y
RBANS-Updateh,aa	х									х						x					х					Х	xy		x ^y
ADCS-ADL-MCI ^{h,aa}			x							X						X					х					х	x ^y		x ^y
Serum PK sample(s) ^{j, bb}			х	Х	х	х	х	х		х			х			x			х		х			x		Х		х	Х
Serum sample for ADA ^{h,bb}			X	x		X		X		X			X			X			x		х			x		х		x	X
Plasma sample for PD biomarkers ^h	x		X	X	X	X	X	X		x			X			X			х		х			x		x		x	X
PrecivityAD TM -Aβ blood test ^{kk}	x																												
Whole blood sample for mRNA ^h			х	х						х						х										х			х
Blood sample for WGS ^h			х																										
APOE e4 testing	х																												
Whole blood sample for other targeted genomic variants ^{h,cc}			x																										

AL002 Alector, Inc.

Table 9: Schedule of Assessments – Part 1 (Study Week 9 and Following) and Part 2 (All Visits) (Continued)

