Study Period	Screening (Days -78 to -23) ^{ss}	Predose Baseline (Days -22 to -1)											Т	`reat	ment													Follow-ı	пр
Study Week ^a			1 (D1)	3 (D15)	5 (D29)	9 (D57)	13	17	21	25	29	33	37	41	45	49	53	57	61	69 and 69	73	77	81	85	89 and 93	76	EFU/4 weeks ^{qq}	SFU/8 weeks ^d	ETc
Visit Window ⁰⁰			p ⊊∓	p \$ =	p ⊊∓	p 2∓	p ⊊∓	p \$ =	p ⊊∓	p ⊊∓	p ⊊∓	±5d	±5d	±5d	p\$∓	p ⊊∓	p ⊊∓	p⊊∓	+ 5d	±5d									
		Part 2	2 onl	ly									For	parti	cipaı	ıts ra	ındo	mize	d un	ler P	arts	1 an	nd 2						
Amyloid PET ^{dd,ll,mm}	х																												
LP for CSF pTau/Aβ42 ^{ff,ll}	х																												
LP for CSF (mandatory for Part 1; optional for Part 2 participants) ^{ff,ll,mm}		x ^{gg}														x					x						x ^{ee}		x ^{ee}
Tau PET (optional)k,hh,ll		х														х					х						x ⁱⁱ		x ⁱⁱ
Longitudinal Amyloid PET (optional) ^{k,ll,mm}	x	х														х											x ⁱⁱ		x ⁱⁱ
WLSA ^{jj,aa} (optional)		Х			х	X	X	X	х	X	х	X	X	X	X	X	X	X	X	X	X	X	X	X	X	х	\mathbf{x}^1		\mathbf{x}^1

Aβ=amyloid beta; AB42=amyloid beta 1-42; ADA=anti-drug antibody (-ies); ADAS-Cog13=Alzheimer's Disease Assessment Scale-Cognitive Subscale; ADCOMS=Alzheimer's Disease Composite Score; ADCS ADL-MCI=Alzheimer's Disease Cooperative Study-Activities of Daily Living – Mild Cognitive Impairment Scale; AE=adverse event; AESI=adverse event of special interest; APOE e4=apolipoprotein E epsilon4; BP=blood pressure; C-SSRS=Columbia-Suicide Severity Rating Scale; CD33=sialic acid-binding Ig-like lectin 3; CDR=Clinical Dementia Rating; COA=clinical outcome assessments; CSF=cerebrospinal fluid; d or D=day; ECG=electrocardiogram; ET=early termination; EFU=efficacy follow-up; FU=follow-up; Ig=immunoglobulin; LP=lumbar puncture; MMSE=Mini-Mental State Examination; MRI=magnetic resonance imaging; mRNA=messenger RNA; PD=pharmacodynamic(s); PE=physical examination; PET=positron emission tomography; PK=pharmacokinetic(s); pTau=phosphorylated tau; RBANS-Update=Repeatable Battery for the Assessment of Neuropsychological Status-Update; RDVF=Research Diagnostic Verification Form; SAE=serious adverse event; SFU=safety follow-up; TMEM106b=transmembrane protein 106b; TPTD=treatment period termination date; TREM2=triggering receptor expressed on myeloid cells 2; WGS=whole genome sequencing; WLSA=Winterlight Labs Speech Assessment; WOCBP=woman of childbearing potential.

a Study Day number and Study Week number begin with 1 on the day of the first administration of study drug.

AL002 Alector, Inc.

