- Perform/collect prior to dosing. For all post-screening MRIs, the MRI should occur at least 5 days prior to the next dose administration and no more than 10 days prior to the next dose administration, with results received from the central imaging vendor prior to dosing. Note that the central imaging vendor typically requires 5 business days after receipt of the MRI before sending a BMW to the site. MRIs may be scheduled outside of the prescribed window, with approval from the Medical Monitor. The Sponsor may request that additional unscheduled MRIs be performed for the detection and follow-up of ARIA. Participants with MRI evidence of ARIA should be managed according to instructions provided in Table 7.
- Vital signs include temperature, respiratory rate, pulse rate, and systolic and diastolic BP while the participant is at rest in a supine position for at least 3 minutes. Heart rate and BP measurements should be obtained with a validated digital monitoring device where available and an appropriately sized cuff. The same arm should be used for all BP measurements if possible. Heart rate and BP should not be measured unless 15 minutes have passed since the last blood draw.
- Perform/collect prior to dosing, and at the end of the infusion. Vital signs will be collected and concomitant medications and AEs documented prior to and at the end of infusion. Triplicate ECGs will be performed predose and 60 to 90 minutes after the end of infusion on Day 1, Weeks 5, 13, 25, and 49. On dosing visits, serum PK samples will be collected predose and within 15 minutes after the end of infusion. On the dosing visits for Day 1 and Weeks 1, 5, 9, 13, 25, and 49 serum PK samples will also be collected 60 to 90 minutes after the end of infusion. On non-dosing visits, serum PK samples may be collected at any time during the visit.
- k Urine pregnancy test (WOCBP only) and vital signs will be performed and concomitant medications and AEs will start being collected at the Predose Baseline Visit and subsequent visits for those participants participating in a Tau PET scan or Amyloid PET scan
- Assessment is to be completed only if visit is conducted for another reason (eg, COAs).

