- Complete PE includes evaluation of the head, eyes, ears, nose, and throat, and the cardiovascular, dermatological, musculoskeletal, respiratory, and gastrointestinal systems. Breast, rectal, and genitourinary exams should be performed as clinically indicated. Limited exams should include cardiovascular, respiratory, and gastrointestinal systems. Symptom-directed PEs may also include any other pertinent system as required.
- ⁿ Perform a limited, symptom-directed PE at specified timepoints or as clinically indicated.
- Includes any medication (eg, prescription drugs, herbal or homeopathic products, vitamins, minerals, vaccines, topical medications, and over-the-counter medications) used by a participant from 14 days prior to initiation of study drug to the final study visit.
- Participants will be randomized prior to undergoing procedures or assessments at the Predose Baseline Visit and Day 1 Visit. Participants requiring a Predose Baseline Visit will be randomized prior to the Predose Baseline Visit. All other participants will be randomized prior to the Day 1 Visit.
- ^q AEs, AESI, and SAEs will be assessed after the participant signs the informed consent until the end of study participation. Any unresolved AEs, AESI, and SAEs will be followed up through resolution or return to baseline. Additionally, SAEs considered related to study drug, [¹⁸F]MK-6240 radiotracer which occur at any time during the study will be reported until resolution, participant withdrawal of consent, loss to follow-up, or death, whichever is applicable. Definitions describing what is and is not considered an AE are provided in Section 7.1.
- Triplicate 12-lead ECGs will be obtained approximately 1-3 minutes apart and before blood draws (predose) on appropriate days. Each ECG must be performed after the participant has been resting (supine) for 10 minutes.

AL002 Alector, Inc.

- s A WOCBP must have a negative serum pregnancy test at screening. Additional blood or urine tests will be performed for further confirmation of nonchildbearing potential if required by local regulations, guidelines, or the institutional review board/independent ethics committee.
- t Urine pregnancy test (for WOCBP only) is to be completed only if optional Tau PET imaging is completed at this visit.

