- If an LP and an MRI are performed in the same visit, either (a) the MRI should be performed first or (b) the MRI should be performed at least 3 days after the LP. This minimizes the effect of CSF removal on brain volume measurements. If an LP and a PET scan are performed in the same visit, either (a) the LP should be performed first or (b) the LP should be performed at least 12 hours after the PET scan. Participants who undergo both Tau PET and Amyloid PET exams at a given study visit must receive these exams on different calendar days. Participants who are electing to undergo longitudinal Amyloid PET scanning will require a new Amyloid PET at screening or at the Predose Baseline Visit; historical Amyloid PET scans may not be used for as part of longitudinal Amyloid PET scanning. Tau and Amyloid PET imaging is allowed outside of the standard visit window by ±35 days. Extensions for PET imaging beyond that window may be permitted, at the discretion of the Sponsor. Tau PET scans or Amyloid PET scans should not be performed If local restrictions for radiation exposure would be exceeded; if applicable, the site should contact the Sponsor to discuss alternative timing of Tau PET or Amyloid PET exams.
- mm If a participant opts into longitudinal Amyloid PET imaging, only a single Amyloid PET exam should be performed prior to dosing on Day 1. A screening Amyloid PET scan may be used both for study inclusion and as the baseline scan for longitudinal Amyloid PET imaging only if the screening Amyloid PET scan was not a historical Amyloid PET scan. If the screening Amyloid PET scan was historical and collected prior to the screening period, the participant will be required to undergo a new Amyloid PET scan at the screening or Predose Baseline Visit. PET imaging is allowed outside of the standard visit window by ±14 days.
- nn Only required at Week 69
- oo Visits may be conducted over 2 consecutive days
- pp Triplicate ECG tracings from Day 1 and Week 25 or Week 49 for approximately 100 consecutive participants will be read by a core ECG laboratory (Note: Central ECG reads may not occur in real time; thus, these results will not be used for safety assessments during study conduct.). Results from centrally read ECG's will not be captured in the eCRF.

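### After screening, every scheduled pregnancy test depends on optional PET, so a woman of childbearing potential without PET has no protocol-mandated test on Day 1, during treatment or at follow-up unless local rules add one

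*Protocol*

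**What the plan says.** Criterion 7c in Protocol 4.1 sets one test for every woman of childbearing potential, serum at screening, and sends the reader elsewhere for the rest: "Additional requirements for pregnancy testing during and after study intervention are described in the Schedules of Assessments".

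The schedules are Tables 8 and 9 in Protocol 14.1. In Table 8 (Part 1) the only mark after screening is at the Predose Baseline Visit. Footnote p places that test "at the Predose Baseline Visit and subsequent visits for those participants participating in a Tau PET scan". In Table 9 the marks at Predose Baseline and Weeks 49 and 73 carry footnote k, which covers that visit and "subsequent visits for those participants participating in a Tau PET scan or Amyloid PET scan". The marks at the efficacy follow-up (EFU), SFU and ET visits carry footnote t: "Urine pregnancy test (for WOCBP only) is to be completed only if optional Tau PET imaging is completed at this visit". Day 1 is unmarked in both tables.

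Footnotes o (Table 8) and s (Table 9) require the screening serum test to be negative and leave room for local practice: "Additional blood or urine tests will be performed for further confirmation of nonchildbearing potential if required by local regulations". The same sentence also names guidelines and the ethics committee.

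Protocol 7.12.2 requires study drug to stop immediately on pregnancy. Criterion 7b requires contraception until 12 weeks after the last dose.

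**The concern.** Whether a woman is tested during treatment depends on whether she opted into imaging, not on whether she receives study drug. Someone eligible, exposed and not having PET can follow the schedule exactly and never be tested after screening. The stopping rule in 7.12.2 then has no mandated test to trigger it. The first infusion is exposed too, because weeks can pass between the screening test and Day 1.

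There is also a smaller drafting problem. Footnote k covers Tau and Amyloid PET, while footnotes p and t name Tau PET only. The Longitudinal Amyloid PET row in Table 9 carries footnote k and is marked at EFU and ET, where the pregnancy-test marks carry footnote t. A site cannot tell whether to test an Amyloid-only participant at those visits.

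**Working it through.** **The plan's own figure.** Protocol 3.1.4 gives up to 13 doses over 48 weeks and up to 25 over 96 weeks. Dosing is every 4 weeks from Day 1, so doses = weeks/4 + 1: 48/4 + 1 = 13 and 96/4 + 1 = 25. Both agree.

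**Pregnancy-test marks, each read with its footnote.**

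| Table | Visit | Footnote | Who is tested |
|---|---|---|---|
| 8 | Screening | o | all women of childbearing potential |
| 8 | Predose Baseline | p | Tau PET only |
| 9 | Screening | s | all women of childbearing potential |
| 9 | Predose Baseline, Weeks 49 and 73 | k | Tau or Amyloid PET |
| 9 | EFU, SFU, ET | t | Tau PET done at that visit |

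Table 9 has 7 marks: 1 unconditional and 6 that depend on PET. Table 8 has 2: 1 unconditional and 1 that depends on PET. Without PET, mandated tests after screening number 0.

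**Does other text fill the gap?**
- Protocol 6.1 names pregnancy testing in a general predose list. The same list names viral serology, which is screening-only, so the list does not set visits.
- Table 4 (Protocol 6.5.10) names serum and urine tests but no visit.
- Protocol 14.4.4.1 is a minimum set for visits shortened by COVID-19.
- SAP 6.3.11.1 speaks of serum tests for all such women at scheduled visits but refers back to the protocol schedules, where the later tests are urine and depend on PET.

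**Time from screening to Day 1.** Screening lasts up to 8 weeks: 8 × 7 = 56 days. With a Predose Baseline Visit, which can also occur for lumbar puncture or speech assessment, 56 + 22 = 78 days. This matches the Day -78 bound in the tables. The sponsor may extend screening.

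**Current span without a mandated test, Day 1 to SFU.** SFU is 8 weeks after the last treatment visit, so it falls at Week 49 + 8 = 57 or Week 97 + 8 = 105. The spans are 57 - 1 = 56 weeks and 105 - 1 = 104 weeks.

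**With the proposed tests.**
- 48-week participant: Weeks 1, 29, 49 and SFU at 57. That is 4 tests, with intervals of 28, 20 and 8 weeks.
- 96-week participant: Weeks 1, 29, 49, 53, 73, 81 and SFU at 105. That is 7 tests, with intervals of 28, 20, 4, 20, 8 and 24 weeks.
- Extension entrants have no SFU (Protocol 3.3.4): 4 - 1 = 3 and 7 - 1 = 6.
- Infusions with a same-day predose test: 3 of 13 or 6 of 25.

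**Urine already collected.** Urinalysis in Table 9 is marked on Day 1, at Weeks 29, 53 and 81, and at SFU and ET. That is 6 of the 8 proposed points; only Weeks 49 and 73 need a new sample.

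**The case against.** The strongest reply is that this is a permissible design choice with several safeguards. Women of childbearing potential must test negative at screening and use hormonal contraception or an intrauterine device with a second method, or abstain. They are told to report pregnancy at once. At every visit they are asked about changes in well-being, hospitalisation and medication (Protocol 7.6.1). Criterion 9 requires a study partner with frequent contact, for example about 10 hours a week, who supplies information at visits. Protocol 1.3 names no embryo-fetal hazard, and local rules may already add tests. The eligible age of 50 to 85 makes the group small. All of this stands and limits severity, but none of it puts a mandated test on the schedule.

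Three stronger readings are tempting but not supported:
- A reader might infer that 7c makes a promise the schedules break. It says only that further requirements are described there, and some are. It sets no frequency and does not say that every such woman will be tested.
- A reader might infer that detection rests on the recall of memory-impaired participants alone. The study partner and the questioning at each visit rule that out.
- A reader might infer that the SFU mark can never apply, because Tau PET is not scheduled there. Footnote ll says "Tau and Amyloid PET imaging is allowed outside of the standard visit window by ±35 days" and lets the sponsor allow more. EFU is only 4 × 7 = 28 days before SFU, so a delayed scan could fall there.

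**Conclusion.** The gap is real on the text. A woman of childbearing potential without PET has one protocol-mandated pregnancy test, at screening, then none over 13 to 25 planned infusions and follow-up, unless local rules add some. The dose counts are planned totals for the shortest and longest treatment periods.

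Severity is low to moderate. The documents do not state how many women are affected, what local rules require, or what the Investigator's Brochure says about reproductive risk, so the practical size cannot be calculated. Nothing in the primary analysis moves: alpha, power and the planned summaries are unaffected, and SAP 7.5.11.1 only lists pregnancy results. The case for acting is that the remedy is cheap and ties testing to drug exposure.

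**What to change.** In the pregnancy-test rows and footnotes of Tables 8 and 9, require a urine test for all women of childbearing potential regardless of PET: predose on Day 1 and at Weeks 29, 49, 53, 73 and 81, and at SFU and ET. Keep the extra tests at PET visits. Reword footnotes p and t to cover Amyloid PET, as footnote k does. Align SAP 6.3.11.1 to serum at screening and urine thereafter.

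The cost is some footnote and SAP wording plus a few urine tests in a small group at existing visits, with an added sample only at Weeks 49 and 73. The change leaves 10 of 13 or 19 of 25 infusions without a same-day test. A team wanting full cover would need a test at every dosing visit.
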